8.2 Secondary Outcome

Secondary outcome measures to be examined are length of stay, relationship between pre-operative PVR and POUR, correlation of baseline IPSS and POUR, relationship of surgical time to POUR, and time to first spontaneous void.

9.0 Potential Risks

The study drug, tamsulosin, is generally considered safe with few side effects. The risk of improper disclosure of private medical information is possible, but is no greater than that inherent in the everyday practice of medicine. Potential risks will be disclosed as part of the informed consent process.

9.1 Side Effects of tamsulosin

Specific side effects of tamsulosin and their reported frequency are[16] :

Greater than 10%:

- Orthostatic hypotension (first dose: 6% to 19%; symptomatic orthostatic hypotension (chronic therapy) <1%)
- Headache (19% to 21%), dizziness (15% to 17%)
- Ejaculation failure (8% to 18%)
- Infection (9% to 11%)
Rhinitis (13% to 18%)

1% to 10%:

- Drowsiness (3% to 4%), insomnia (1% to 2%), vertigo (\leq 1%)
- Loss of libido (2%)
- Diarrhea (6%), nausea (4%)
- Weakness (8% to 9%), back pain (7% to 8%)
- Blurred vision (\leq 2%)
- Pharyngitis (6%), cough (3% to 5%), sinusitis (4%)

Less than 1% (Limited to important or life-threatening):

- Epistaxis, exfoliative dermatitis, hypersensitivity reaction, hypotension, intraoperative floppy iris syndrome (IFIS), palpitations, priapism, syncope

With the exception of IFIS, all of these potential side effects are reversible. These and all other adverse effects, expected and unexpected, will be documented and reported.

9.2 Serious Adverse Events

Any event occurring while a patient is on study that meets the following criteria will be considered a Serious Adverse Event:

- Death
- Life-threatening (i.e. immediate risk of death)
- Readmission or prolongation of existing hospitalization
- Persistent or significant disability/incapacity

Important adverse events that may not result in death, may not be life –threatening, or do not require hospitalization may be considered serious when they may acutely jeopardize the patient without immediate medical attention to prevent one of the

outcomes listed above. Serious may also include any other event deemed as such by the investigator.

All serious adverse events will be monitored by clinical and/or research staff. The relationship of the adverse event to the study drug will be categorized as Not related, Unlikely to be related, Possibly related, Probably related and Definitely related. All serious adverse events will be reported to the IRB and DSMB within 5 days.

In the case of a serious drug-related adverse event, study drug will be discontinued and patients will continue to be followed.

9.3 Confidentiality

Each study subject will be assigned a unique study ID number, which will be linked to their identifying information by a key. This linking key will be kept separate from the data collection forms, locked and secure in the study coordinator's office. Study findings will be summarized and presented in a manner in which individuals will not be identifiable.

9.4 Data Safety Monitoring Board

This study will use a Data Safety Monitoring Board (DSMB). Details of the DSMB for this study are contained in the attached DSMB Plan.

10.0 Analytic Methods

10.1 Data collection

Data will be collected prospectively by study staff in the office, at the bedside and through Epic chart review. A study ID will be assigned to each patient and study documents will all use this ID to collect data. Identifiable data will be stored separately. Baseline variables to be collected will include basic demographics, past medical history and medication list, PVR and IPSS. Operative data will include type and duration of surgery, fluid intake, medications given, and any perioperative urinary catheterization. Data will be recorded postoperatively will include fluid balance, need for urinary catheterization, pain medication and adverse events.

All data will be recorded on a data collection sheet (see attached data sheet). PVR and IPSS done in the MMP NSS office will also be recorded on separate forms (see attached PVR and IPSS forms), which will be linked to the primary data collection sheet. These data sheets will be stored in a locked and secure area of the study coordinator's office.

RedCap, a HIPAA-compliant database, will be used to store all information after it is collected. Data entry and access will only be allowed to research coordinator and Principal Investigator.

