2.0 Background

In the United States, estimates of POUR rates range from 2% to 70%[1, 2]. This wide range is due to multiple factors affecting its incidence, including anesthetic regimen, duration and type of surgery, age, gender, co-morbidities and presence of pre-operative urinary symptoms[2]. There is a paucity of literature specific to spine patients, but published rates in this population range from 5% to 38%[3-5]. POUR can be painful, physically damaging, and emotionally troubling for patients.

Up to 22% of patients that develop POUR receive an intra-urethral catheter[6], which places them at an increased risk of developing hospital-acquired urinary tract infections. These catheter-associated urinary tract infections (CAUTIs) significantly contribute to patient morbidity, increase the average length of hospital stay, and are associated with increased inpatient mortality[2, 7]. CAUTIs also have a significant financial impact, costing U.S. hospitals an estimated \$400 million annually[8]. This is especially significant since the Centers for Medicare and Medicaid no longer compensate hospitals for the additional cost of treating CAUTIs, believing them to be reasonably preventable[9].

The exact pathogenesis of POUR is not well understood. One theory is that over-activation of alpha-adrenergic nerve receptors on the human bladder is an important contributor to urinary retention after surgery[10]. This theory is based on current understanding of bladder physiology and the fact that many agents such as ephedrine used during general anesthesia have activity at alpha-adrenergic receptors. Patients treated with ephedrine have been shown to be at increased risk of developing urinary retention [11, 12].

Tamsulosin, a medication that blocks these alpha-adrenergic receptors, has been shown to significantly reduce the incidence of POUR in specific surgeries when given preoperatively[13-15]. This drug, which is FDA approved and widely used to treat symptoms of bladder outlet obstruction and benign prostatic hypertrophy (BPH) in males, has a favorable side effect profile and a half-life of 9-15 hours, achieving steady state after 5 days with daily dosing[16]. While previous studies have demonstrated the practicality, efficacy, and safety of prophylactic tamsulosin for POUR, the trials were small and only examined urinary retention in patients undergoing hernia repair and other general surgical procedures; no spinal surgery patients were included in these trials.

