Madani and colleagues had the largest trial, randomizing 232 male patients undergoing inguinal or scrotal surgery to either tamsulosin or placebo[14]. While they found that tamsulosin dramatically reduced the incidence of POUR (5.9% with tamsulosin vs 21.1% with placebo; $p = .001$), the patient population differs from our spine patients. This study also excluded patients with excessive perioperative fluid intake and duration of surgery greater than 90 minutes, both of which are populations at risk for POUR and therefore should be studied. Mohammadi-Fallah and colleagues found a similar reduction in POUR in their randomized trial (2.5% with tamsulosin vs 15% with placebo; $p = .04$), though the numbers were very small ($n=80$) and the patient population underwent inguinal herniorrhaphy[13]. Both of these studies administered study drug no more than 14 hours prior to surgery. The third and most recent study by Poylin and colleagues was a retrospective review in men undergoing pelvic surgery; tamsulosin was given at the discretion of the surgeon 3 days prior to surgery[15]. Their findings were in line with previous work, with a rate of POUR of 6.7% in the tamsulosin group and 25% in the control group ($p = .029$). In none of these studies were there complications or adverse events attributable to tamsulosin.

At Maine Medical Center (MMC), there are approximately 2600 elective spinal surgeries annually. Nearly half of these patients are males over age 50, who have an increased risk of developing POUR[3]. Over the past three years, over 1900 males aged 50 years or greater have undergone elective spinal surgery at MMC, and within this group approximately 17% have developed POUR.

Currently, the administration of preoperative prophylactic tamsulosin is standard practice at MMP Orthopedics, given to high risk male patients who are undergoing total joint replacement. A modified version of the International Prostate Symptom Score is administered preoperatively, and if the score is ≥ 6 , these patients are given a course of tamsulosin (3 days preop and continuing 7 days after discharge). Although they have no formal data, providers and nursing staff believe the incidence of POUR has decreased substantially, and aside from occasional episodes of transient hypotension, there have been no safety issues with this practice.

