3.0 Study Objectives

3.1 Primary Objective

This trial will test the hypothesis that prophylactic administration of tamsulosin will reduce the incidence of POUR compared to placebo, and will not increase the risk of adverse events in this setting.

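### Hypotension under anesthesia has no measurement item in section 10.1 and no between-arm comparison in 10.3, although the primary objective includes no added harm in the surgical setting

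*Combined protocol and SAP*

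**What the plan says.** Section 3.1 states a two-part hypothesis: prophylactic tamsulosin "will reduce the incidence of POUR compared to placebo, and will not increase the risk of adverse events in this setting". Section 6.2 has the patient take study drug every evening from five days before surgery up to the night before it.

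Section 10.1 describes what is collected. For the operation: "Operative data will include type and duration of surgery, fluid intake, medications given, and any perioperative urinary catheterization". For the period afterwards: "Data will be recorded postoperatively will include fluid balance, need for urinary catheterization, pain medication and adverse events". The second list is the only one in 10.1 that names adverse events, and neither list has a blood pressure item. The only blood pressure reading the protocol specifies is the orthostatic measurement at the office visit (6.2), before the first dose. Section 10.1 also refers to an attached data sheet, which is not in the text available for review.

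Section 9.1 lists hypotension among the drug's effects and adds a general commitment: "These and all other adverse effects, expected and unexpected, will be documented and reported". Section 9.2 treats a qualifying event at any time on study as serious. Section 10.3 sets out the comparison of POUR, length of stay and time to first void; it names no comparison of any safety measure.

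**The concern.** Blood pressure is the safety signal to which the protocol gives most attention. Orthostatic hypotension is an exclusion with its own screening measurement (5.2, 6.2), and the account of local orthopedic practice in section 2.0 says that "aside from occasional episodes of transient hypotension, there have been no safety issues with this practice". By design the men come to anesthesia soon after a dose of an alpha-blocker. Yet the operative data list, which covers the hours when the drug meets anesthesia, contains no pressure measurement.

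A fall in pressure that is treated and corrected in the operating room need not meet any criterion in 9.2. Whether it is written down as an adverse effect is left to the judgment of whoever is charting, with no definition to go by. The safety half of 3.1 would then rest, for that period, on unstructured reporting. A general adverse-event comparison added to 10.3 would not cure this, because its intraoperative input would still be unstructured.

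There is a second, conditional reason. Section 2.0 says: "Patients treated with ephedrine have been shown to be at increased risk of developing urinary retention". If the tamsulosin arm were to receive more ephedrine, part of any benefit on retention could be offset. A table of vasopressor use by arm would help a reader to interpret the POUR result, and none is planned.

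**Working it through.** **1. The plan's own figure.** Section 10.2 gives 264 per group for 0.170 against 0.085, two-sided 0.05, 80% power, continuity-corrected. With mean proportion 0.1275 and difference 0.085:

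- Uncorrected: n₀ = [1.960·√(2×0.1275×0.8725) + 0.842·√(0.170×0.830 + 0.085×0.915)]² / 0.085² = 240.5, that is 241.
- Corrected: n = (n₀/4)·[1 + √(1 + 4/(n₀×0.085))]² = 263.5, that is 264.

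The stated 264 is reproduced. Nothing proposed here changes it.

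**2. Exposure at surgery.** Section 2.0 gives a half-life of 9 to 15 hours. If surgery is 12 hours after the last dose (an assumption), the fraction of that dose remaining is 0.5^(12/9) = 0.40 to 0.5^(12/15) = 0.57, ignoring carry-over from earlier doses. This shows that the men are exposed under anesthesia; it does not measure an effect on pressure.

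**3. Where a pressure fall under anesthesia would be recorded.**

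| Source | Covers the operation? | Structured measure? | Compared by arm? |
|---|---|---|---|
| 10.1 operative list | Yes | Medications (would include vasopressors) and fluids; no pressure | No |
| 10.1 postoperative list | Unclear: the wording may refer to when data are recorded | No definition of hypotension | No |
| 9.1 adverse effects | Yes, no time limit | No definition or threshold | No |
| 9.2 serious events | Yes, if a criterion is met | Criteria for seriousness only | No |
| Attached data sheet | Not visible | Not visible | 10.3 names no comparison |

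**4. What 264 per group could show.** The documents give no rate of vasopressor use or hypotension under anesthesia, so a range is assumed. The half-width of the 95% interval when both arms have rate p is 1.96·√(2p(1−p)/264). At p = 0.30 this is 1.96·√(0.42/264) = 0.078. The detectable increase is the one giving 80% power at two-sided 0.05 without continuity correction.

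| Assumed placebo rate | 95% half-width (points) | Detectable increase (points) |
|---|---|---|
| 5% | 3.7 | 6.7 |
| 10% | 5.1 | 8.5 |
| 20% | 6.8 | 10.6 |
| 30% | 7.8 | 11.7 |
| 40% | 8.4 | 12.1 |
| 50% | 8.5 | 12.1 |
| 60% | 8.4 | 11.5 |

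For lowest pressure as a continuous measure, the half-width is 1.96·SD·√(2/264) = 0.17 SD; the SD is not in the documents.

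**The case against.** The strongest reply is that the plan does cover these events. Section 9.1 names hypotension and promises that all adverse effects will be documented, with no limit to the postoperative period. Section 9.2 applies throughout the study. Vasopressors fall under the operative medications. The lists in 10.1 are not worded as exhaustive, and the sentence on postoperative data is garbled enough to describe when data are written down, not when events happen. The data sheet may already hold a pressure field.

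All of this stands, and it rules out a stronger reading that a reader might draw from 10.1: that the trial leaves hypotension under anesthesia out altogether, or that nothing is collected during the operation. The documents do not support that. Nor do they support saying that a null POUR result could not be examined against vasopressor use, since the medications are collected; what is missing is the tabulation by arm.

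Two further limits also stand. The 6% to 19% in 9.1 is a first-dose orthostatic figure and does not describe the day of surgery, which follows several doses; the same section puts symptomatic orthostatic hypotension on chronic therapy, and hypotension itself, below 1%. Section 2.0 reports no tamsulosin-attributable events in the three earlier studies. And no statement in the documents shows that treated falls in pressure go unreported, or that men on tamsulosin need more vasopressor; both are inferences.

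What the reply does not meet is the absence of a definition, a visible pressure item and any planned comparison. A pressure field on the data sheet would supply the measurement but still leave 10.3 without an analysis.

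**Conclusion.** The point holds as a gap in structured measurement and analysis, not as a failure to capture. In the visible plan, harm under anesthesia would be judged from general adverse-effect reporting and, indirectly, from the medications record, with no comparison by arm, although 3.1 places freedom from added harm in the primary hypothesis.

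Its size cannot be stated as a bias, because the documents give no rate of intraoperative hypotension. What can be stated is what the remedy would deliver: an interval of about ±8 points and a detectable rise of about 12 points at assumed vasopressor rates of 30% to 60%. That is informative but coarse; a 12-point rise is larger than the 8.5-point reduction in POUR that the trial is sized for (17.0 − 8.5). With no margin set for acceptable harm, a non-significant difference would not establish the safety claim. This is a worthwhile, inexpensive improvement. It does not threaten the primary POUR comparison.

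**What to change.** In 10.1, unless the data sheet already has them, add to the operative data the lowest intraoperative systolic or mean pressure (choose one in advance) and vasopressor given: yes/no, drug, total dose. Abstract them from the anesthetic record during the Epic chart review already planned.

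In 10.3, name both as safety outcomes for 3.1 and compare them by randomized arm, with a difference and 95% interval, next to a general adverse-event comparison. Read the two together, because treatment with a vasopressor raises the pressure that is then recorded. Show vasopressor use by arm beside the POUR result, but do not adjust the primary comparison for it: it arises after randomization and may be a consequence of treatment.

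Word the safety conclusion as an estimate with its interval, not as a demonstration that no harm was added.

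The cost is two or three fields per man, abstracted by existing staff, and a sentence or two in 10.3. The downside is minor abstraction work and a safety summary that may look less favorable. No visit, procedure, patient or aspect of clinical care is added or changed.

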10.2 Sample Size and Power Calculations

Tamsulosin is hypothesized to reduce POUR compared to placebo in males. Observational data from our center shows a POUR rate of about 17% in patients similar to those to be included in the trial. We hypothesize that the use of the drug can reduce this rate by 50%. A two group continuity corrected c^2 test with a 0.050 two-sided significance level will have 80% power to detect the difference between a control group proportion of 0.170 and a treatment group proportion of 0.085 (odds ratio of 0.454) when the sample size in each group is 264 and a total sample size of 528.

We anticipate recruiting 264 evaluable patients in each group who took at least one dose of study drug and who also had surgery. Due to expected patient drop-out (from surgery cancellations, patients changing their mind or forgetting to take study drug), we expect to enroll up to 610 patients to achieve this.

In a recent chart review, it was found that 670 potentially eligible male patients (age 50-85 and not on preoperative tamsulosin) were seen at MMP NSS in FY 2014, and 680 were seen in FY 2015. Given this volume of patients undergoing spine surgery at MMC, it seems reasonable to expect we could accrue our target enrollment in three years.

10.3 Randomization

To evaluate the success of randomization, characteristics of patients in the treatment and control groups will be compared using t-tests or their non-parametric equivalents, as appropriate, for continuous variables and chi-square tests or Fisher's exact tests, as appropriate, for categorical variables. The primary outcome, incidence of POUR, will be compared across groups using chi-square tests. If large baseline imbalances between groups are found, a secondary analysis will be performed using a logistic regression model, with POUR as the outcome variable, treatment group as the predictor of interest, and imbalanced patient characteristics as confounding variables. Secondary objectives examine the relationship between other factors and POUR and will be analyzed similarly. Length of stay and time to first void will be analyzed as continuous variables, using t-tests and linear regression models.

REFERENCES

1. Wu, A.K., A.D. Auerbach, and D.S. Aaronson, *National incidence and outcomes of postoperative urinary retention in the Surgical Care Improvement Project*. Am J Surg, 2012. **204**(2): p. 167-71.
2. Baldini, G., et al., *Postoperative urinary retention: anesthetic and perioperative considerations*. Anesthesiology, 2009. **110**(5): p. 1139-57.
3. Boulis, N.M., et al., *Urinary retention following routine neurosurgical spine procedures*. Surg Neurol, 2001. **55**(1): p. 23-7; discussion 27-8.
4. Jung, H.J., et al., *Postoperative urinary retention following anterior cervical spine surgery for degenerative cervical disc diseases*. Clin Orthop Surg, 2013. **5**(2): p. 134-7.

5. Gandhi, S.D., et al., *Patient and surgical factors associated with postoperative urinary retention after lumbar spine surgery*. Spine (Phila Pa 1976), 2014. **39**(22): p. 1905-9.
6. Burger, D.H., et al., *Prevention of urinary retention after general surgery: a controlled trial of carbachol/diazepam versus alfuzosine*. J Am Coll Surg, 1997. **185**(3): p. 234-6.
7. Hooton, T.M., et al., *Diagnosis, prevention, and treatment of catheter-associated urinary tract infection in adults: 2009 International Clinical Practice Guidelines from the Infectious Diseases Society of America*. Clin Infect Dis, 2010. **50**(5): p. 625-63.
8. Scott, R.D. *The Direct Medical Costs of Healthcare-Associated Infections in U.S. Hospitals and the Benefits of Prevention*. 2009 [cited 2015 November 24, 2015].

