6.2 Outpatient procedures

After patient consent is obtained, all study patients will undergo a non-invasive post-void bladder scan via portable ultrasound to measure PVR. In addition, study staff will obtain a modified International Prostate Symptom Score (IPSS), a short survey to measure baseline lower urinary tract symptoms[17].

At this time, patients will also have orthostatic blood pressure measurements taken as follows:

- BP and pulse taken while patient is laying down and sitting
- BP and pulse taken after patient goes from sitting to standing

If patient meets definition of having orthostatic hypotension as described in 5.2 Exclusion Criteria, he will be excluded from study participation. A record of all patients screened and excluded for this reason will be kept with study documents. After PVR, BP and IPSS, patient will be given prescription for 7 days of study drug. Patient will be instructed to begin once daily evening administration of study drug five days prior to surgery, and to continue self-medication up to and including the night before surgery. Patients will record study drug administration on a drug diary card, given by office staff. Patient will be instructed to keep two doses at home for possible dosing after surgery, depending on discharge date. Patient and office providers will be blinded to the assigned medication.

Computer-generated 1:1 randomization (without blocking) will be done by the MMC pharmacy, which will place a seven day supply of tamsulosin 0.4 mg or placebo in sequentially numbered envelopes corresponding to study ID prior to study start. Study drug will be kept in and dispensed from locked cabinet in research coordinator's office. Study staff will access locked cabinet and pull next available envelope to give to consented patient. Study ID number will be logged into study binder kept in locked cabinet.

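### Replace the adjusted model triggered by an undefined 'large' baseline imbalance with a covariate-adjusted comparison of POUR fixed in advance and always fitted

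*Combined protocol and SAP*

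**What the plan says.** All references are to the combined protocol and SAP.

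- **Primary test (10.3):** "The primary outcome, incidence of POUR, will be compared across groups using chi-square tests". No covariates enter it.
- **Adjusted analysis (10.3):** "If large baseline imbalances between groups are found, a secondary analysis will be performed using a logistic regression model". The model has POUR as outcome and treatment as the predictor of interest, with "imbalanced patient characteristics as confounding variables". The same section judges balance by significance tests on baseline characteristics. It gives no threshold for *large*, and nothing elsewhere supplies one.
- **Baseline data (10.1):** "Baseline variables to be collected will include basic demographics, past medical history and medication list, PVR and IPSS".
- **Timing (6.2):** "After PVR, BP and IPSS, patient will be given prescription for 7 days of study drug". PVR and IPSS are therefore measured before study drug is handed over. Allocation is 1:1 without blocking, and no stratification is described.
- **Prognosis (2.0):** the factors said to affect POUR include "duration and type of surgery, age, gender, co-morbidities and presence of pre-operative urinary symptoms".
- **Secondary questions (3.2 and 8.2):** the relation of PVR and of IPSS to POUR is left open, so the documents do not say how strongly either predicts it.

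**The concern.** Under proper randomisation a baseline imbalance is chance. Its size says nothing about whether the characteristic predicts POUR, so it is a poor rule for choosing covariates: a large difference in an irrelevant variable would enter the model, while a strong predictor that happened to balance would be left out.

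Because *large* is undefined and no covariates are named, both the existence and the content of the adjusted result are open to judgement once data are in hand. An analysis of that kind cannot serve as a clean check on the primary result. Meanwhile, pre-treatment variables that the protocol itself considers relevant to POUR go unused in the treatment comparison unless the trigger happens to fire.

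**Working it through.** **1. Reproduce the plan's sample size.** Section 10.2 states: "A two group continuity corrected c^2 test with a 0.050 two-sided significance level will have 80% power", for 17% against 8.5%, with 264 per group. With p̄ = 0.1275 and difference d = 0.085:

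- n′ = [1.960·√(2·0.1275·0.8725) + 0.8416·√(0.17·0.83 + 0.085·0.915)]² / 0.085² = 240.5, i.e. 241 per group without correction.
- With correction: n = (n′/4)·[1 + √(1 + 4/(n′d))]² = 263.5, i.e. **264**, as stated.
- Approximate power at 264 per group: 80.1% with the continuity correction, 83.5% without.

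**2. How often chance fires the trigger.** The thresholds are assumptions, since the plan gives none. Covariates are treated as independent, 264 per arm.

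- p<0.05, three covariates: 1 − 0.95³ = 14.3%. With ten covariates: 1 − 0.95¹⁰ = 40.1%.
- Standardised difference: its SD is √(2/264) = 0.087. P(|d|>0.10) = 0.251, so 1 − (1 − 0.251)³ = 57.9%. P(|d|>0.20) = 0.0216, so 1 − (1 − 0.0216)³ = 6.3%.

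**3. Room for a fixed model.** Expected events are 264 × (0.17 + 0.085) = 67.3. Four terms (treatment, age, IPSS, PVR) leave 67.3/4 = 16.8 events per term, which is adequate.

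**4. Power of always adjusting.** Simulated trials, 8,000 per setting, 264 per arm, marginal rates held at 17% and 8.5%. Three independent standard normal covariates of equal strength stand in for age, IPSS and PVR. The adjusted test is the likelihood-ratio test of treatment; the comparator is the uncorrected chi-square. The AUC is the assumed joint discrimination of the covariates.

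| AUC | Chi-square | Adjusted | Gain, points (SE) |
|---|---|---|---|
| 0.50 | 84.4% | 84.4% | 0.0 (0.1) |
| 0.60 | 84.7% | 85.1% | 0.4 (0.2) |
| 0.64 | 84.6% | 85.6% | 1.0 (0.2) |
| 0.70 | 84.1% | 86.3% | 2.2 (0.3) |
| 0.75 | 83.6% | 87.9% | 4.3 (0.3) |
| 0.80 | 85.0% | 90.3% | 5.3 (0.3) |

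A separate simulation using a Wald test (4,000 trials per setting, Monte Carlo error about 0.6 points) gave 84.0% → 83.5% with useless covariates, 85.2% → 86.1% at an odds ratio of 1.5 per SD, and 84.3% → 89.6% at 2.0.

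**5. Type I error.** With 12.75% in both arms, chi-square and adjusted rejection rates were 5.04%/5.19% (AUC 0.50), 5.05%/5.04% (0.64) and 5.75%/5.74% (0.75), Monte Carlo SE about 0.25 points. The last pair is high for both tests alike. A 12,000-trial run at comparable strength (log odds ratio 0.6 per SD) gave 5.3% for both, so simulation noise is the likely explanation.

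**6. Missing baselines.** Suppose PVR and IPSS are each missing in 5% (assumption).

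| AUC | Chi-square, all patients | Adjusted, complete cases | Adjusted, mean-imputed |
|---|---|---|---|
| 0.64 | 84.6% | 82.0% | 85.5% |
| 0.70 | 84.1% | 82.9% | 86.3% |

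Dropping patients would more than cancel the gain at these strengths; simple imputation preserves it.

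**7. Scale of the effect.** The marginal odds ratio is (0.085/0.915)/(0.17/0.83) = 0.454. The corresponding conditional odds ratio is 0.434 with covariates at 1.5 per SD and 0.398 at 2.0. The adjusted odds ratio is thus a different quantity from the one used for sizing.

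**The case against.** The strongest reply is that no primary conclusion is exposed. The chi-square is fixed, untriggered and is the kind of test the trial was sized on; the triggered model is labelled secondary. Selection follows baseline differences rather than outcomes, so the latitude is narrower than a free choice of result. This stands, and it is why the point is an improvement rather than an error. It does not supply a definition of *large*, a covariate list or a time at which they are settled.

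Covariate strength is not in the documents. The exclusions in 5.2 (alpha-blocker use, prior prostate, bladder or urethral surgery, indwelling catheter, renal failure) plausibly narrow the range of PVR and IPSS. This also stands: the AUC rows of 0.75 and 0.80 deserve little weight, and the gain may be near zero.

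The no-cost claim depends on the test. With a Wald test and useless covariates about 0.5 points were lost, within simulation error. The amendment should therefore name the likelihood-ratio test. The simulations also used independent, normal, correctly modelled covariates; skewed PVR was not examined.

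Section 6.2 has PVR and IPSS obtained in all study patients, so the 5% missingness is only a precaution. Type of surgery and co-morbidities are also named in 2.0, so the three-covariate list involves judgement. What matters most is that the list is fixed in advance.

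**Conclusion.** The point holds as a low-cost improvement. The unadjusted primary test is valid and adequately powered. The only adjusted treatment comparison, however, depends on an undefined chance imbalance. Depending on how *large* is read, its probability of existing runs from 6% to 58% for the same three covariates.

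The firm argument is the removal of that discretion. The power argument is secondary and conditional: nothing lost with a likelihood-ratio test if the covariates are uninformative, about 1 point gained at AUC 0.64, 2 to 3 at 0.70, and more only at strengths the documents do not support. Any power gain reaches the primary result only if the adjusted model is made primary. Against the continuity-corrected test used for sizing the advantage looks larger, but most of that comes from dropping the correction.

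**What to change.** Amend section 10.3, dated and before unblinding, to specify:

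- **Model:** logistic regression of POUR on treatment, age, IPSS and PVR, fitted whatever the observed balance, with functional forms fixed in advance (for example log(PVR + 1)) and treatment tested by likelihood ratio.
- **Role:** primary, with the chi-square as support; or at minimum a mandatory supportive analysis with the chi-square kept primary. State which.
- **Estimate:** standardised risk difference with 95% CI, so the marginal comparison is kept, and the odds ratio labelled as conditional.
- **Missing baselines:** for example, single imputation of PVR or IPSS by the mean pooled over both arms, so no patient is dropped.
- **Baseline table:** descriptive, which still allows a check for allocation problems. No significance tests or imbalance trigger to choose covariates.
- **Exclusions from the model:** surgery duration and fluids, which arise after randomisation.

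The cost is the amendment and the drafting of these rules. No extra data or patients are needed, and 264 per group stands. Making the model primary does change the primary analysis method, which is why the standardised risk difference is needed.
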